### 3.2 Number of Subjects

Ten subjects will be enrolled in this trial.

### 3.3 Duration of Participation

Length of study treatment will be 4 weeks. Per treatment schema, patients will have 5 total visits including initial pre-operative evaluation (visit 1); surgical excision procedure (visit 2) and follow-up visits at postoperative week 2 and 4, and month 3. Patients will receive a phone call 24 hours following their surgical excision to assess adverse events. Another phone call will be made at postoperative weeks 1 and 3, and postoperative month 2.

### 3.4 Primary Study Endpoints

**Aim #1:** Identify the type and number of serious adverse events related to TP in PCCA PP compared to PCCA PP base alone following surgical scar excision. While we do not anticipate any severe adverse events, we will monitor for the following:

- Skin infection
- Skin irritation
- Wound dehiscence
- Clinically significant abnormalities in physical examination and vital signs.

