**Study Summary**

Title	Double Blind, Single-Center, Randomized, Within-Subject Placebo, Phase I Study Evaluating the Effects of Topical Pentamidine in Prevention of Hypertrophic Scar Formation
Running Title	Novel Topical Gel for Hypertrophic Scar Prevention
IRB Protocol Number	17-005230
Phase	Pilot Study
Methodology	Double Blind, Single-Center, Randomized, Within-Subject Placebo Phase I Study
Overall Study Duration	3 months
Subject Participation Duration	3 months
Single or Multi-Site	Single site
Objectives	Evaluate safety of topical pentamidine (TP) as an adjuvant to surgical scar excision (SSE) in the treatment of hypertrophic scar formation. Safety will be measured by serial monitoring for adverse events following the procedure and during treatment duration. Secondarily, study will evaluate drug quality and standardizations as well as investigate initial signs of efficacy.
Number of Subjects	10
Diagnosis and Main Inclusion Criteria	Hypertrophic scar diagnosed in Mayo Clinic Department of Dermatology or Division of Plastic Surgery, Rochester, Minnesota.
Study Product, Dose, Route, Regimen	Pentamidine, delivered as topical formulation containing 2% TP in silicone-containing base, PCCA Pracasil™-Plus (PP), versus placebo base alone. Approximately 1.8 mL of product in allotted single dose containers will be applied every 48 hours for 4 weeks following surgical scar excision.
Duration of Administration	Once every 48 hours for 4 weeks.
Reference therapy	SSE with silicone compounding base only (PCCA PP).
Statistical Methodology	The primary analysis will use descriptive statistics to document adverse events between treated and untreated lesions. The secondary analysis will use paired t-test or Wilcoxon signed rank test to compare the change in lesion height and characteristics between the treated and placebo groups following SSE (TP + PCCA PP vs. PCCA PP alone). In addition, two-factor analysis of variance (ANOVA) with repeated measures on both factors will be used to evaluate the effect of treatment and follow-up time for other continuous measures such as Vancouver Scar Scale (VSS) and Patient and Observer Scar Assessment Scale (POSAS).

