## 7 Statistical Plan

### 7.1 Sample Size Determination

This is a first in-human exploratory study to determine the efficacy of topical pentamidine. There will be 80% power to detect an effect size of 1.3 standard deviations for the comparison of MED between any two treatment groups. This calculation is based a two-sided unpaired t-test with a type I error of 0.05.

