### 7.2 Statistical Methods

#### Primary Hypothesis

This primary hypothesis will be evaluated by paired t-test.

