## Non-serious Adverse Events

- skin ulcers
- erythema
- reaction at site of administration
- rash

Routine monitoring of safety evaluation includes an active assessment of local tolerability (e.g. erythema, edema, vesication, necrosis, ulceration etc.) using an acceptable scale called the local skin reaction (LSR) grading scale as outlined below [30].

Grade	0	1	2	3	4
Erythema					
	Not present	Slightly pink <50%	Pink or light red >50%	Red, restricted to treatment area	Red extending outside treatment area
Flaking/Scaling					
	Not present	Isolated scale, specific to lesions	Scale <50%	Scale >50%	Scaling extending outside treatment area
Crusting					
	Not present	Isolated crusting	Crusting <50%	Crusting >50%	Crusting extending outside treatment area
Swelling	Not present	Slight, lesion specific oedema	Palpable oedema extending beyond individual lesions	Confluent and/or visible oedema	Marked swelling extending outside treatment area
Vesiculation/ Pustulation					
	Not present	Vesicles only	Transudate or pustules, with or without vesicles <50%	Transudate or pustules, with or without vesicles >50%	Transudate or pustules, with or without vesicles extending outside treatment area
Erosion/ Ulceration					
	Not present	Lesion specific erosion	Erosion extending beyond individual lesions	Erosion >50%	Black eschar or ulceration

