**8.2 Recording of Adverse Events**

At each contact with the subject, the study team must seek information on adverse events by specific questioning and, as appropriate, by examination. Information on all adverse events should be recorded immediately in the source document, and also in the appropriate adverse event section of the case report form (CRF). All clearly related signs, symptoms, and abnormal diagnostic, laboratory or procedure results should be recorded in the source document.

All adverse events occurring during the study period must be recorded. The clinical course of each event should be followed until resolution, stabilization, or until it has been ultimately determined that the study treatment or participation is not the probable cause. Serious adverse events that are still ongoing at the end of the study period must be followed up, to determine the final outcome. Any serious adverse event that occurs during the Adverse Event Reporting Period and is considered to be at least possibly related to the study treatment or study participation should be recorded and reported immediately.

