### 8.3.1 Sponsor-Investigator reporting: notifying the Mayo IRB

The sponsor-investigator will report to the Mayo IRB any UPIRTSOs and Non-UPIRTSOs according to the Mayo IRB Policy and Procedures.

According to Mayo IRB Policy any serious adverse event (SAE) which the Principal Investigator has determined to be a UPIRTSO must be reported to the Mayo IRB as soon as possible but no later than 5 working days after the investigator first learns of the problem/event.

Information collected on the adverse event worksheet (and entered in the research database):

- Subject's name:
- Medical record number:
- Disease/histology (if applicable):
- The date the adverse event occurred:
- Description of the adverse event:
- Relationship of the adverse event to the research (drug, procedure, or intervention\*):
- If the adverse event was expected:
- The severity of the adverse event: (use a table to define severity scale 1-5\*\*)
- If any intervention was necessary:
- Resolution: (was the incident resolved spontaneously, or after discontinuing treatment)
- Date of Resolution:

All adverse events will be recorded in the Case Report Form. The sponsor-investigator will review all adverse events to determine if reports need to be made to the IRB and FDA. The sponsor-investigator will sign off on any adverse events that are reported in the Case Report Form within 24 hours. For this protocol, only directly related SAEs/UPIRTSOs will be reported to the IRB.

We will use of a table to define Relationship of an Event to the Research and to define the severity of each event.

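### The primary safety endpoint and its analysis are stated inconsistently, no listed form item ties a local event to a scar end, and vital signs named in Aim 1 are scheduled only before surgery

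*Combined protocol and SAP*

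**What the plan says.** - **Section 3.4 (primary endpoint, Aim 1):** "Identify the type and number of serious adverse events related to TP in PCCA PP compared to PCCA PP base alone". The items to be monitored include skin irritation and abnormal vital signs.
- **Study Summary, Statistical Methodology:** "The primary analysis will use descriptive statistics to document adverse events between treated and untreated lesions". There is no restriction to serious or related events. It continues: "The secondary analysis will use paired t-test or Wilcoxon signed rank test", applied to lesion height and characteristics.
- **Section 7.2, Primary Hypothesis:** the whole text is "This primary hypothesis will be evaluated by paired t-test". No hypothesis or variable is given. Section 7.1, just before it, opens: "This is a first in-human exploratory study to determine the efficacy of topical pentamidine".
- **Section 8.1, Non-serious Adverse Events:** lists skin ulcers, erythema, rash and "reaction at site of administration". Tissue necrosis is listed as serious.
- **Section 8.2:** "All adverse events occurring during the study period must be recorded".
- **Sections 3.6 and 8.3.1:** list the case report form source data and the adverse event worksheet items. Neither list has an item for scar end. The Relationship Index in 8.3.1 grades relatedness to the investigational drug only.
- **Section 6.11:** physical examination and vital signs (blood pressure, pulse, temperature, respiratory rate) are marked at Visit 1 only.

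**The concern.** Safety is the primary goal of this study (Section 2), so the reader needs to know which events make up the primary result, how they are compared between products, and whether they will be measured. The plan leaves each of these partly open. The same ten patients could yield a nearly empty primary result under Section 3.4, which itself expects no severe events, or a full table of local reactions under the Summary. The comparison between products, which is the reason for treating both ends of one scar, depends on knowing which end reacted. If that is not captured when the event happens, it may not be recoverable later. One component of Aim 1 has no scheduled measurement once application has begun.

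**Working it through.** **1. The plan's own figure.** Section 7.1 claims 80% power for 1.3 SD with a two-sided unpaired t-test at 0.05. It gives no group size. I assume 10 per product, from the ten subjects in Section 3.2, each contributing one scar end to each product. Then df = 2 × 10 − 2 = 18, noncentrality = 1.3 × √(10/2) = 2.91, and power = 0.785, close to the stated value. The outcome named is MED, which is not among the endpoints in 3.4 or 3.5. The figure therefore does not bear on adverse events, and it suggests that Section 7 was written for efficacy or carried over from elsewhere.

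**2. The statements of the primary result, side by side.**
- Section 3.4: serious and related events only, TP against base; no method stated.
- Summary: all adverse events, descriptive, with the comparator called untreated. Under Sections 1.6.5, 3.1 and 5.2 the comparator end receives base. The only untreated part is the 1–2 cm border zone, which is not a comparison arm.
- Section 7.2: paired t-test, variable unstated. The Summary assigns this test to the secondary analysis.

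No text says which statement governs.

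**3. What Section 3.4 excludes if followed literally.** An event must meet a serious criterion in 8.1 to count. Erythema, rash, skin ulcers and site reactions are classed there as non-serious. Skin irritation, listed under Aim 1, belongs with these, so 3.4 also conflicts with itself. Some local events stay in: tissue necrosis, and any event that meets another serious criterion.

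**4. The link from event to product.**
- Every subject uses both products over the same period (3.1).
- Subjects and clinical investigators are masked (5.6).
- Relatedness is graded to the investigational drug, not to TP or base separately (8.3.1).
- Containers are labelled by scar end (5.5), so the end is the only key to the product for a local event.
- The worksheet lists 11 items: name, record number, disease, date, description, relationship, expectedness, severity, intervention, resolution and resolution date. None is scar end. The source data list in 3.6 has none either.
- Section 8.1 plans the local skin reaction (LSR) scale but does not say that each end is scored separately.

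Systemic events cannot be assigned to a product by scar end.

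**5. Vital signs.** The relevant visits are Visit 3 (week 2, on treatment) and Visit 4 (week 4, end of treatment). The vital signs row in 6.11 is marked at 0 of these 2. Sections 6.6 and 6.8 detail both visits without mentioning vital signs. ECGs at both visits give heart rate. Blood pressure, respiratory rate and measured temperature remain without a planned measurement.

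**6. Two lesser mismatches in timing.** Section 8.1 extends systemic safety evaluation to Visit 5, where 6.11 marks adverse event evaluation but no laboratory studies, ECG or neuropsychiatric assessment. Section 8.1 also runs follow-up for 3 months from the last application, whereas Visit 5 is 3 months from surgery. With the first application on day 1 and one every 48 hours, the last falls on day 1 + 2(n − 1): day 27 for 14 applications (5.3) or day 31 for 16 (upper end of 3.1). The reporting period therefore ends nominally 27 or 31 days after Visit 5.

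**The case against.** The strongest reply is that little turns on this in a ten-patient descriptive pilot. All events must be recorded whichever definition governs, no success decision hangs on the endpoint, the word serious in 3.4 may be a drafting slip, and the Summary's next sentence correctly calls the comparator placebo. All of that is fair. It shows that the data will mostly exist; it does not settle which of them form the primary result.

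Several stronger readings are tempting, and the documents do not support them.
- *The plan will test adverse events with a t-test.* A reader might infer this from 7.2 and note that the test is undefined if no event occurs. But 7.2 never says that its hypothesis concerns safety, and no section proposes a t-test on event indicators. P-values from such a test would not measure the harm of the present wording. Nor would the upper confidence limit for zero events in ten, which rewording does not change.
- *Local events cannot be assigned to a product.* This goes too far. The forms themselves are not in the documents, only lists of their contents. The free-text description, the subject's treatment log, which also records adverse events (5.4), and scar photographs (6.11) may show the site. What holds is that no listed item requires it.
- *No vital sign is measured on treatment.* ECGs supply heart rate, fever is asked about and self-monitored (1.6.1), and a clinical examination could include vital signs in practice. Counting telephone contacts, the day of surgery or Visit 5, which may be by telephone, as missed measurements would inflate the gap.
- *Events after Visit 5 are lost.* Section 8.1 follows unresolved events and tells subjects to report later ones they believe may be related, so this is partly covered.

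**Conclusion.** The point holds and should be fixed. There are two incompatible definitions of the primary safety endpoint, in 3.4 and the Summary, plus an unfinished sentence in 7.2 that is probably efficacy or carried-over text but still contradicts the Summary on what the primary analysis is. Following 3.4 literally excludes most local reactions from the primary endpoint while they continue to be recorded. Attribution of local events to a product rests on incidental capture of scar end. Of the vital signs in Aim 1, three of four (blood pressure, respiratory rate, measured temperature) have no planned measurement at Visits 3 and 4.

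This rests on taking the listed form contents and the schedule as complete; a form that already has a site field would remove that part. No event rate is assumed, and no numerical bias is claimed. The timing mismatches are minor.

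**What to change.** - Use one definition in 3.4, the Summary and 7.2: type and number of all adverse events, with serious and related events reported as subsets, summarised descriptively.
- State in 7.2 that the paired t-test belongs to the efficacy analysis. In the Summary, call the comparator base-treated.
- Add one item per adverse event: proximal, distal or not site-specific. Compare products within patient for site-specific events only. Report systemic events, laboratory values and ECG for the whole group against baseline.
- State that the LSR scale already planned in 8.1 is scored separately for each scar end.
- Record vital signs at the existing Visits 3 and 4, so that the schedule matches Aim 1.
- Reconcile the Visit 5 systemic evaluation and the reporting period in 8.1 with Sections 6.10 and 6.11.

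The cost is wording in three sections, a few added form items, LSR scored twice per visit, and vital signs at two visits already in clinic. The reported event count will look less favourable because non-serious events count, and the primary safety result will carry no p-value. The restriction to completers in 7.3 is a separate matter that this change does not resolve.

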## Adverse Event

An untoward or undesirable experience associated with the use of a medical product (i.e. drug, device, biologic) in a patient or research subject.

The safety evaluation of this topical drug product during the conduct of a clinical trial includes an assessment of systemic safety as well as evaluation of local safety. Evaluation of systemic safety addresses warnings, precautions, and adverse events from approved product labeling for pentamidine isethionate (e.g., laboratory studies including renal and hepatic function, hematology, blood glucose, and calcium; periodic cardiac monitoring with electrocardiogram [ECG], and assessment for neuropsychiatric adverse events [including confusion and hallucinations]. The evaluation of systemic safety will be conducted at baseline (Visit 1, pre-operative), during treatment (Visit 3, Week 2), and after treatment (Visit 4, Week 4) and extended follow-up (Visit 5, Month 3). The local safety evaluation includes an active assessment of local tolerability (e.g. erythema, edema, vesication, necrosis, ulceration etc.) using an acceptable scale called the local skin reaction (LSR) grading scale [30]. The LSR grading scale uses a 0-4 numerical rating, with clinical descriptor and representative photographic images for each rating. The scale provides the ability to rate each LSR category (erythema, flaking/scaling, crusting, swelling, vesication/postulation and erosion/ulceration) and generate a composite objective LSR score [30].

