## Serious Adverse Events

Adverse events are classified as serious or non-serious. Serious problems/events can be well defined and include;

- death
- life threatening adverse experience
- hospitalization
- inpatient, new, or prolonged; disability/incapacity
- persistent or significant disability or incapacity
- birth defect/anomaly
- tissue necrosis

[figure not shown]
and/or per protocol may be problems/events that in the opinion of the sponsor-investigator may have adversely affected the rights, safety, or welfare of the subjects or others, or substantially compromised the research data.

All adverse events that do not meet any of the criteria for serious, should be regarded as **non-serious adverse events**.

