#### \* Relationship Index

The relationship of an AE to the Investigational Drug is a clinical decision by the sponsor-investigator (PI) based on all available information at the time of the completion of the CRF and is graded as follows:

1. Not related: a reaction for which sufficient information exists to indicate that the etiology is unrelated to the study drug; the subject did not receive the study medication or the temporal sequence of the AE onset relative to administration of the study medication is not reasonable or the event is clearly related to other factors such as the subject's clinical state, therapeutic intervention or concomitant therapy.
2. Unlikely: a clinical event, including laboratory test abnormality, with a temporal relationship to drug administration which makes a causal relationship improbable and in which other drugs, chemicals, or underlying disease provide plausible explanations.

3. Possible: a clinical event, including laboratory test abnormality, with a reasonable time sequence to administration of the drug but which could also be explained by concurrent disease or other drugs or chemicals; information on drug withdrawals may be lacking are unclear.

4. Probable: a clinical event including laboratory test abnormality, with a reasonable time sequence to administration of the drug, unlikely to be attributed to concurrent disease or other drugs or chemicals and which follows a clinically reasonable response on withdrawal (de-challenge): re-challenge information is not required to fulfill this definition.

5. Definite: a reaction that follows a reasonable temporal sequence from administration of the drug, or in which the drug level has been established in body fluids or tissues, that follows a known or expected response pattern to the suspected drug, and that is confirmed by improvement on stopping or reducing the dosage of the drug, and reappearance of the reaction on repeated exposure (re-challenge).

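### The primary safety endpoint in Section 3.4 counts only related serious events, disagrees with the Study Summary and Section 7.2, and leaves the graded local skin reaction score without any analysis

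*Combined protocol and SAP*

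**What the plan says.** Three places define the primary safety question, each differently.

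- Section 3.4, Aim 1: "Identify the type and number of serious adverse events related to TP in PCCA PP compared to PCCA PP base alone". The next sentence reads "While we do not anticipate any severe adverse events, we will monitor for the following", followed by a list that includes skin infection, skin irritation and wound dehiscence.
- Study Summary, Statistical Methodology: "The primary analysis will use descriptive statistics to document adverse events between treated and untreated lesions". This is limited neither to serious nor to related events.
- Section 7.2: "This primary hypothesis will be evaluated by paired t-test". Neither the hypothesis nor the variable is given.

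Section 8.1 decides what counts as serious. Its list is death, life-threatening events, hospitalization, disability, birth defect and "tissue necrosis", plus events that the sponsor-investigator judges serious. The non-serious list holds skin ulcers, erythema, rash and "reaction at site of administration".

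Section 8.1 also adopts the LSR scale for local tolerability: six categories, each graded 0 to 4, with a composite. Of the scale it says "The scale provides the ability to rate each LSR category". A local safety evaluation is scheduled at Visits 3 and 4 (Sections 6.6, 6.8 and 6.11). LSR does not appear in the endpoints (3.4, 3.5), the source data list for the CRF (3.6), the Study Summary methods or Section 7.

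**The concern.** Safety of topical pentamidine (TP) against base is the stated primary question. Each patient receives both agents, with the scar end randomised, so local reactions are what the design compares best. Section 3.4 sets most of them aside by requiring an event to be serious.

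It also requires the event to be related. The Relationship Index in Section 8.3.1 allows a grade of not related when an event is clearly due to other factors, among them "therapeutic intervention or concomitant therapy". Surgery is an available alternative explanation for infection or dehiscence after excision. Randomisation of the ends makes case-by-case attribution unnecessary for a comparison of local events, and filtering on it could remove part of a real excess at the TP end.

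Two things are at stake. The analyst has no single definition of the primary safety result. And a graded local score is obtained but never used for the question it was chosen to inform.

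**Working it through.** **The plan's own figure.** Section 7.1 states 80% power for 1.3 SD with a two-sided unpaired t-test at 0.05. Normal approximation: n per group = 2(1.960 + 0.842)² / 1.3² = 15.70 / 1.69 = 9.3, rounded up to 10. Exact noncentral-t power with 10 per group is 78.5%, so the figure reproduces to within two points. It refers to a variable called MED, which is not defined, and to an unpaired test. It says nothing about the safety endpoint.

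**What the Section 3.4 endpoint captures.** Skin irritation is on the Section 3.4 monitoring list. Site reactions, rash, erythema and skin ulcers are non-serious under Section 8.1. Such an event therefore reaches the endpoint only through tissue necrosis, another listed seriousness criterion or the sponsor-investigator's judgement.

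**Chance of no events at either end.** Inputs: 10 subjects (Section 3.2), two treated ends each, so 20 sites. The documents give no rate, so let p be an assumed probability of a related serious event per site, equal at both ends, with sites independent. Then P(0 versus 0) = (1 − p)^20.

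| Assumed p per site | P(0 versus 0) |
|---|---|
| 0.5% | 90.5% |
| 1% | 81.8% |
| 2% | 66.8% |
| 3% | 54.4% |
| 5% | 35.8% |
| 10% | 12.2% |

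The probability is one half at p = 1 − 0.5^(1/20) = 3.4%. If only the TP end could have an event, the corresponding value is 1 − 0.5^(1/10) = 6.7% per patient.

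**What zero of 10 excludes.** One-sided 95% upper limit: 1 − 0.05^(1/10) = 25.9%. Upper limit of the two-sided exact 95% interval: 1 − 0.025^(1/10) = 30.8%.

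**A test on paired event counts.** An exact sign (McNemar) test with k discordant pairs, all in one direction, has p = 2 × 0.5^k. Five pairs give 0.0625 and six give 0.031. At least six of the 10 patients would have to be discordant, all the same way.

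**A paired LSR difference, if scored by end.** The 95% half-width in SDs of the paired differences is t(0.975, n − 1)/√n.

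| Pairs | Half-width (SD) | Difference with 80% power, paired t-test (SD) |
|---|---|---|
| 10 | 2.262/3.162 = 0.72 | 1.00 |
| 9 | 2.306/3.000 = 0.77 | 1.07 |
| 8 | 2.365/2.828 = 0.84 | 1.16 |

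Fewer than 10 pairs is a realistic case, because Section 7.3 keeps only subjects who complete every procedure. The documents give no SD for LSR, so these widths cannot be turned into score points.

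**The case against.** A reader might infer that the whole primary safety comparison will come out 0 versus 0. The documents do not support that. The Study Summary describes adverse events without restriction, and a table of irritation, infection and dehiscence after excision need not be empty. The sentence in Section 3.4 says *severe*, which the Severity Index in Section 8.3.1 treats separately from *serious* in Section 8.1. The two words seem to be used interchangeably in 3.4, but that is a reading. The 3.4% threshold rests on an assumed rate.

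A reader might also infer that LSR is already collected for each end and merely left unanalysed. No section says that the two ends are scored separately. The CRF itself is not in the documents and Section 3.6 is only a list. It includes physical examination, under which LSR could be entered. LSR is therefore unspecified, not shown to be missing.

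Nor is LSR the only measure able to show a difference. Section 3.6 lists erythema, erosions, scabbing, skin ulcer, pain and pruritus as adverse events, and Section 1.6.4 says that risks will be quantified with VSS and POSAS.

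On attribution, the index requires other factors to be *clearly* responsible, and Section 8.2 has every adverse event recorded whatever its cause. A tendency to blame surgery is possible but cannot be shown.

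These points limit the concern without removing it. The Study Summary does not settle the matter, since it conflicts with Sections 3.4 and 7.2 and refers to untreated lesions although the comparator end receives base. Neither the Section 3.6 list nor the adverse event worksheet in Section 8.3.1 has an item for scar end, so even a comparison of all events by end is not secured.

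**Conclusion.** The concern holds in a limited form. Section 3.4, the Study Summary and Section 7.2 give three incompatible accounts of the primary safety variable and its analysis. Taken literally, the Section 3.4 endpoint omits most of the local reactions under monitoring. For that endpoint alone, no events at either end is more likely than not if the per-site rate is below about 3.4%, assuming equal rates and independent sites. A result of 0 of 10 would still be compatible with a true rate of up to 25.9% (one-sided) or 30.8% (two-sided). The LSR composite has no stated role in any endpoint, listed CRF item or analysis. All of this can be put right by better specification. It does not show that the trial cannot describe local safety.

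**What to change.** - In Section 3.4, the Study Summary and Section 7.2, state one comparative local-safety summary in the same terms: all local adverse events tabulated by randomised scar end, TP against base, whatever their judged relatedness, with relatedness and seriousness as descriptors. Name the variable for any test kept in Section 7.2, and use *serious* and *severe* as Sections 8.1 and 8.3.1 define them.
- In Section 3.6 and on the CRF, record scar end for each local event, and LSR by end at Visits 3 and 4.
- Report the paired TP-minus-base LSR difference with its 95% confidence interval as a supporting safety result. Name one of the two visits in advance as the main one.
- Give exact 95% limits beside patient-level counts of serious events. Each patient receives both agents, so a systemic event cannot be assigned to an end.

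The cost is protocol wording, one CRF page and scoring two ends at examinations that are already scheduled. The reference cited for the LSR scale concerns actinic keratosis therapy, and its suitability for fresh excision wounds is not argued in the plan. LSR should therefore support the event table and not replace it. Making it the lead primary result would be a debatable choice that this point does not require.
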